Moreover, the oral ARG inhibitor (CB-1158) have been well-tolerated in a phase I trial (*ClinicalTrials.gov identifier (NCT number): NCT02903914*) (see Risk Evaluation). All in all, it appears very unlikely that the ARG1-18,19,20 peptide vaccine will initiate a general overactivation of the immune system.

Preclinical development: We conducted an exploratory study with vaccination of mice with the humane sequence of ARG1-18,19,20. The mice did not present immune responses to the human sequence. Similar results were obtained in murine vaccine studies with human sequence of PD-L1. The murine organs have been reviewed by a pathologist without any sign of organ damage (See “Preclinical exploratory study of vaccination ARG1 peptides in C57Bl6 mice with Montanide ISA-51” appendix 09)

Adjuvant

A peptide antigen is administered with an immune enhancer known as an adjuvant. The adjuvant increases the uptake of the antigen by APCs, and mediates so-called “danger signals” to the APC.

When an APC takes up and presents antigen in the context of a danger signal, it will deliver co-stimulatory signals to T cells, which activates T cells that recognize the antigen.

The adjuvant to be used is Montanide ISA-51. Montanide is an incomplete Freund's adjuvant (IFA) which forms water in oil emulsion when mixed with an aqueous phase. It is commercially available from Seppic S.A, France, which maintains a Drug Master File. Montanide has been used in cancer vaccines in other research projects in more than 5000 patients corresponding to more than 50.000 injections subcutaneously or intramuscularly. IFA is used with success in combination with long peptides, where clinically relevant responses can be produced with IFA. For instance in a vaccine with a long HPV-16 peptide against vulva cancer ⁵²⁻⁵⁴

Montanide has a well-documented safety profile. Frequently reported side effects after injection are flu-like symptoms (headache, chills, fever and nausea) while most common local reactions are granuloma, local pain, inflammation or erythema. These reactions are generally classified as mild to moderate and they are typically transient in nature.

Therapeutic peptide vaccines lack a suitable animal model for safety and dose testing

Therapeutic peptide cancer vaccines are a group of biopharmaceuticals that lack a useful non-human model for nonclinical safety evaluation according to the ICH S6(R1):

1. To identify initial safe dose and subsequent dose escalation schemes in humans
2. To identify potential target organs for toxicity and for the study of whether such toxicity is reversible; and
3. To identify safety parameters for clinical monitoring

According to the guideline it is recommended that safety evaluation is performed in a relevant species where the test material is pharmacologically active alternatively in transgenic animals or by use of homologous therapeutics.

To create an animal model with completely transgenic TCR is not possible. Furthermore, the amino acid sequences of ARG1, the target molecule in question, differ between humans and other animals, making the assessment of potential autoimmunity impossible using an animal model. Accordingly, it is not feasible to use a transgenic animal model to reproduce the pharmacological activity and toxicity that occurs in the human body because of the administration of peptide vaccines.

The numerous limitations on standard preclinical animal studies have been described in a consensus paper by a collaboration of international societies for cancer immune therapy ⁵⁵. This consensus paper underscores that "Even if mice were generated that expressed the appropriate HLA type and the human antigen sequences, such models might not adequately predict safety or autoimmune effects based on the diversity of the other components of antigen processing machinery involved." A clinical development paradigm for cancer vaccines has been proposed by a group of more than 50 experts from academia, regulatory bodies and the biotech/pharmaceutical

industry from Europe and the US FDA⁵⁶. In this development paradigm, it is proposed to "...adopt a flexible approach, performing studies likely to be informative, while avoiding tests that contribute little valuable information" when performing preclinical safety testing of therapeutic cancer vaccines and the combination of cancer vaccines with other agents. Considerations for safety studies have been published⁵⁷. The proposal is to focus on using *in silico* human expression data, and further that it is not feasible to replicate immune responses in animals since immune responses are dependent on human MHC-molecules.

Regarding identification of initial dose, there are likewise no suitable animal models. In the case of peptide vaccination, the dosage should be higher than an unknown threshold level, below which presentation by antigen-presenting cells will not be sufficient. Doses higher than the threshold dose will not increase effectivity, but also do not cause increased toxicity since peptides are rapidly degraded by local peptidases to amino acids. The dosages selected for the current study are based on experience.

In conclusion, studies in animals on safety, characterization of the pharmacokinetics, and determination of maximum tolerated dose (MTD) are not relevant in the case of therapeutic peptide vaccination.

Choice of dosage

Cancer vaccines have emerged as a promising novel modality; however, identifying the maximum tolerated dose has been challenging. In contrast to cytotoxic agents, cancer vaccines modulate the immune system to target specific antigens on cancer cells and/or other immune cells. This mechanism of action is not expected to be directly dose related or to induce severe toxicity.

Most trials that have been conducted testing the safety and efficacy of therapeutic cancer vaccines in dose escalation studies have not provided any correlation between dose escalation and toxicities or immune responses (monitored as cellular response)⁵⁸.

In an analysis of clinical trial design suitable for therapeutic cancer vaccines, Rahma et al. found that the risk of serious toxicities with therapeutic cancer vaccines are extremely low and that toxicities do not correlate with dose levels. Furthermore, the conventional dose escalation design, with few exceptions, is regarded not suitable for cancer vaccines. Therefore, the main goal is to determine a dosage that can create an immune response and the method of defining that dose depends on whether the vaccine belongs to a class of vaccines that has been previously tested in humans. If the vaccine class (e.g. a peptide) has been administered in humans and found to be non-toxic and able to induce immune response, then it is proposed using a dose comparable to the dose used in the previous trials⁵⁸.

Based on our previous clinical experience in the CCIT, administration of either 100 µg or 250 µg generates an intended immunological response measured by analyzing induced vaccine specific cellular response in the treated patients. Especially relevant in these settings is the finding that all the patients with stable disease (SD) who responded to treatment in a NSCLC trial exhibited a detectable vaccine specific T-cell response prior to vaccination (measured by IFN γ ELISPOT assay),

suggesting that the pre-existence of relatively high frequency anti-IDO T-cells in these patients correlate with the clinical efficacy ^{2,59}.

To conclude, therapeutic cancer vaccines are generally expected to have a relatively safe profile and dose-independent efficacy. Based on the above findings, the peptide dosage of a 100 µg of each ARG1-18,19,20 peptide has been chosen for the trial, as this dosage is believed to be relevant to achieve both immunological and clinical responses.

Number of participants

The study is designed as a phase I trial. Ten patients with metastatic solid tumors will be treated. If 3 or more patients experience grade 3-4 AE in phase I associated with the vaccination, the trial will be stopped.

Patient recruitment

Patients will be recruited nationally and included at the Department of Oncology at Herlev Hospital. Patients with metastatic, incurable solid tumors (NSCLC, colorectal cancer, urothelial cancer, breast cancer, ovarian cancer, malignant melanoma, and HNSCC) can be included regardless of what earlier oncological treatment they have received; i.e. surgery, radiation, high-dose IL-2 or experimental treatment.

It is estimated that patient inclusion can be completed within 12 months.

Treating doctors at the departments of oncology can refer patients to the investigator. The investigator reads through the referral material and the patients are then invited to a talk about the protocol at the Department of Oncology at the experimental unit (EFEK).

Information and informed content retrieval

At the first appointment at the experimental unit, patients will be informed orally about the protocol by a doctor with experience in both oncology and immunotherapy under supervision of [name] [name]. The patient is always welcome to bring an assessor (relative, friend etc.) Written patient information in the form of "Participant Information" will be handed out to the patient.

The conversation with the participant takes place in an undisturbed room and 60 minutes is allotted.

The information will be presented in an easily comprehensible language without the use of technical or value-laden terms. The consultation and written information will be in Danish, but in cases of foreign languages a certified translator will be provided.

Information given during the consultation will be based on the written participant information and include the following:

- Predictable risks, side effects, possible complications, disadvantages, as well as the possibility for unpredictable risks and complications
- Other treatment options including advantages and disadvantages, as well as the consequences of no treatment and supportive care
- Private and other confidential information contained in the medical record can be accessed both during and after the treatment. The medical record information will be reviewed by third party officials during the statutory quality assessment of the trial
- Other conditions which might have influence on the patient's decision on participation
- The possibility for the participant to withdraw their informed consent at any time after inclusion

If the participant wishes to participate, a new appointment will be booked where the consent is signed by the doctor and the participant. The new appointment and time of reflection will be within 4-7 days after the first appointment, but if the patient needs more time of reflection this can also be accommodated. If the patient wishes to sign the content at the first appointment this is also acceptable. If the patient fulfills all in- and exclusion criteria the patient will be included and receive treatment immediately after.

After inclusion, the participant will be informed,

- If additional risks, side effects, complications or other disadvantages are discovered during the trial
- If major changes are made to the protocol which might affect health or safety
- If other relevant health conditions are discovered during the trial so forth the participant has not expressed a wish not to receive such information
- About the results achieved and possible consequences to the patient so forth the participant has not expressed a wish not to receive such information
- If the trial is terminated before schedule, the participant will be informed of the reason

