Objectives and endpoints

The primary objective is to assess the safety and tolerability of a peptide vaccine containing the enzyme arginase-1 (ARG1) with Montanide ISA 51 as adjuvant in patients with metastatic and treatment-refractory solid tumors. The primary endpoint is adverse events (AE) assessed by Common Terminology Criteria for Adverse Events (CTCAE) 4.0 and laboratory monitoring.

The secondary objective is to evaluate the immune response before, during and after treatment. The endpoint is responses of ARG1 specific T cells measured by ELISPOT and cytokine release assays.

The exploratory objective is to evaluate the clinical efficacy of the treatment. The endpoints are objective response (OR), progression free survival (PFS) and overall survival (OS).

Protocol synopsis

Background

Metastatic solid tumors are regarded incurable and fatal despite great progresses in medical oncology over the past decade. Treatment options are in end-effect palliative and given with the purpose of prolonging life. Standard therapies for metastatic solid tumors range from hormone suppression to aggressive chemotherapy regimens, but in the last couple of years immunotherapy has revolutionized several cancer treatments. This protocol describes a new approach in the treatment of patients with metastatic solid cancer by modulating the tumor microenvironment using a peptide vaccine.

The unregulated growth of cancer cells is only possible when the immune system does not launch an effective antineoplastic response. Cancer cells highjack the system of checks and balances in the immune system by exploiting the system of local adaptive immune resistance. One mechanism utilized by malignant cells is the overexpression of the immunosuppressive enzyme arginase-1 (ARG1).

ARG1 is an enzyme expressed by some cancer cell lines and different myeloid cells in the immunosuppressive tumor microenvironment. ARG1 catalyzes the conversion of the amino acid arginine to ornithine and urea. A depletion of arginine suppresses T cell function through the impairment of the T cell receptor (TCR)-complex resulting in immunosuppression in a cancer setting.

The theoretic background for a peptide vaccine against ARG1 is to boost the activity of ARG1-specific T cells to eliminate immune cells that express ARG1 as part of the local immunosuppressive microenvironment in cancerous tissues.

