Center for Cancer Immune Therapy (CCIT) has identified spontaneous T cell reactivity against ARG1 peptides in peripheral blood mononuclear cells (PBMCs) of cancer patients and healthy donors. Thus boosting ARG1-specific T cells may directly modulate immune regulation ¹.

Peptide vaccine safety

The potential peptide vaccine-related safety profile is linked to the presence of the target antigen in normal tissue and to the risk of acute anaphylactic reactions.

However, previous peptide vaccination trials have had very mild side effects, no matter which proteins have been targeted (see Risk evaluation). Research groups from CCIT have documented mild side effects testing the indoleamine 2,3-dioxygenase (IDO) peptide vaccine with no CTCAE grade 3 or 4 toxicities ². The ARG1 vaccine and IDO vaccine resemble in many ways. They are both self-proteins with a broad expression and they are lymphocyte suppressive enzymes with an overexpression in immunosuppressive cancer associated immune cells.

Moreover, a phase I trial treating cancer patients with an oral ARG1 inhibitor (CB-1158) presented data on drug related adverse effects in April, 2017. A total of 17 patients with advanced solid tumors were treated with CB-1158, and the drug was generally well tolerated with no drug-related serious adverse events³. Even though the ARG1 peptide vaccine and CB-1158 differ in both mechanism of action and administration they both target the same enzyme. Therefore, the AEs registered for patients treated with CB-1158 could possibly indicate what AEs to expect in the ARG1 trial.

Montanide ISA 51

Montanide ISA 51 can cause local discomfort at the insert site, but does usually not cause any systemic side effects with the dose used in this trial. (See “Product Resume Montanide ISA 51”, appendix 11)

Target population

This protocol describes the treatment of patients with solid metastatic cancers. Despite many treatment advances in cancer therapy, most metastatic solid cancers are still incurable and most patients will at some point find themselves without viable treatment options. The majority of deaths are caused by metastatic solid cancers such as lung, colon, breast, and prostate cancer. Immunotherapy is an established and effective treatment for an increasing number of cancer patients including different metastatic solid cancers.

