The treatment with an ARG1 peptide vaccine has a potential in all metastatic solid cancers with a high concentration of ARG1-expressing cells, such as myeloid-derived suppressor cells (MDSCs) known for their impairment anti-cancer immunity. These tumors include non-small cell lung cancer (NSCLC), colorectal cancer, urothelial cancer, breast cancer, ovarian cancer, malignant melanoma, and squamous cell carcinoma of the head and neck (HNSCC) ^{4,5}. We aim to test the

ARG1 vaccine in patients who have exhausted conventional treatment options. Hence, patients with progressive metastatic solid cancers of the types mentioned above in advanced stages are eligible to enter this protocol.

Number of participants

The study is a phase I trial where 10 patients with metastatic solid tumors will be treated. If 3 or more patients experience grade 3-4 AE associated with the vaccination, the trial will be stopped.

Patient recruitment

The trial is expected to begin the inclusion in August 2018. Patients will be recruited from the Department of Oncology, Herlev & Gentofte University Hospital, but can also be referred from other centers in Denmark. The inclusion period is expected to extend over 12 months.

Treatment plan

Patients included in the trial will be treated with the ARG1 vaccine every third week for 48 weeks. Sixteen vaccines will be given in total.

At the end of vaccination, patients who are not excluded from the protocol because of progression will have follow up appointments after 3 and 6 months in the experimental unit (EFEK), Herlev Hospital.

Assessment of safety

A systematic recording of AEs will take place during the course of treatment and follow up in accordance with the Common Terminology Criteria for Adverse Events (CTCAE). The AEs will be reported by the investigator, who will make a relatedness assessment. Recording will take place during patient attendance in the outpatient clinic or at the hospital ward at the Department of Oncology, Herlev Hospital.

Immunological evaluation

Blood samples

In order to monitor the immune response, ARG1 levels and immune related changes during treatment, project blood samples will be taken before, during and after treatment. Project blood samples will be taken at the follow up appointments after 3 and 6 months.

Tumor biopsy

At baseline and after the 4th vaccine, a tumor biopsy will be performed if the tumor is accessible. The objective is to evaluate the tumor immune microenvironment of each patient.

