During administration of the first 3 vaccines, the patient is observed for 30 minutes with measurements of pulse and blood pressure before and after the vaccine is given. The remainder of vaccines can be administered with observation of the patient for 15 minutes. Patients are observed for acute toxicities in the form of allergic reactions, including anaphylactic shock. Allergic reactions and/or anaphylactic shock will be treated per hospital guidelines.

The vaccines are ordered after contact to the project nurse at the clinical experimental unit (KFE) and to the manufacturing unit. (SOP: "Bestilling og håndtering af ARG1-18,19,20 peptid vaccine til patienter i protokol AA1809", appendix 14). When the vaccine is received, the "receipt of transport" is signed. (SOP: "Transport og udlevering af ARG1-18,19,20 peptid og Montanide, AA1809" appendix 15).

If the patient is prevented in attending the planned treatment day, the treatment can be moved to the following Tuesday or Thursday. If the treatment is postponed more than 6 weeks, patients will be excluded.

Criteria for treatment modifications

Delay of treatment

The treatment will be postponed if the patient experiences non-hematological AE grade ≥ 2 , except fatigue and skin related AEs such as local reaction at the injection site. Otherwise the following criteria are applicable:

Blood samples	Criteria
Leukocytes	$< 1,5 \times 10^9$ (grade 3)
Neutrophilic granulocytes	$< 1,0 \times 10^9$ (grade 3)
Thrombocytes	$< 50 \times 10^9$ (grade 3)
Hemoglobin	$< 5 \text{ mmol/l}$ (grade 3)
Creatinine	$> 3 \times \text{ULM}$ (grade 3)
ASAT	$> 5 \times \text{ULN}$ (grade 3)
ALAT	$> 5 \times \text{ULN}$ (grade 3)
Bilirubin	$> 3 \times \text{ULN}$ (grade 3)
Other AEs	
Skin-related AE	$\geq \text{grade 3}$
Fatigue AE	$\geq \text{grade 3}$
All other AE	$\geq \text{grade 2}$

The treatment will be postponed until CTCAE grade < 2 .

Criteria for end of treatment

1. Unacceptable toxicity (see adverse events)
2. Disease progression
3. On patient request
4. Clinical judgement
5. Other anti cancer treatment. However, radiotherapy treatment of to non target lesions is allowed.
6. Pregnancy
7. Delayed treatment

Unacceptable toxicity:

If treatment related AE grade 3-4 is not reduced appropriately within 12 weeks, the treatment will be stopped and the patient is excluded. Shorter delays can occur multiple times with no consequences for the patient or the trial.

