Patients included in the trial will have additional blood tests performed compared to patients receiving standard treatment. The amount of blood and the specific procedure when taking a blood sample are not associated with any significant risk. There is a minimal risk of bleeding and infection and pain and bruising can occur in the area.

Tumor biopsies will be taken by experienced doctors, and is not associated with any significant risk; again there is a small risk of bleeding and infection and pain and bruising might also occur in the area.

CT scans and PET-CT scans are not considered a risk based on the low dose radiation. Both full body CT and PET-CT scans give a radiation doses of around 15 milliSievert (mSv), which is about 5 times the annual background radiation^{61,62}. The contrast used can very rarely cause allergic reactions and brief reduction in renal function; therefore patients are screened by standard procedures prior to the examination.

Monitoring of toxicity

Adverse events

Adverse events (AE) are defined as any undesirable experience occurring to a subject during a clinical trial, whether or not considered related to the investigational treatment. All AEs reported spontaneously by the subject or observed by the investigator or his staff will be recorded and described in the patient chart and the electronic Case Report Form (eCRF). The severity and consequences will be recorded for each AE. The severity and relation to the study medication will be assessed in accordance with the guidelines described in the following.

The investigator must attempt to identify all clinical and objective events from patients receiving treatment and determine their relation to the study medication. The investigator determines the relationship between AEs and treatment using the following guidelines:

Grading of adverse events

The severity of an AE refers to the intensity of the reaction.

Events are graded using CTCAE version 4.0. The following scale can be used if this grading is not applicable:

- 1 = light
- 2 = moderate
- 3 = severe
- 4 = life threatening
- 5 = lethal

Patients experiencing AEs will be monitored with the relevant clinical evaluations and laboratory investigations assessed by the attending physician. All AEs must be monitored until satisfactory restitution or stabilization. Results of the monitoring must be recorded in the patient chart and eCRF.

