 - fluid treatment or treatment of nausea
 - blood transfusion
 - platelet transfusion
 - febrile leucopenia/neutropenia
 - administration of investigational procedures
 - placement of a permanent intravenous catheter

These events are to be registered in the eCRF.

Known adverse reactions

Montanide ISA-51:

Montanide ISA-51 has been used in more than 150 clinical trials. Montanide has a well-documented safety-profile. Frequently reported side effects after injection are flu-like symptoms (headache, chills, fever and nausea) while most common local reactions are granuloma, local pain,

inflammation or erythema. These reactions are generally classified as mild to moderate and they are typically transient in nature.

Reference is made in attached drug information leaflet (appendix 11).

Arginase peptide:

The peptide has not been tested in humans, so no adverse reactions have been documented.

Handling adverse events

Autoimmune side effects will be handled according to a local guideline for handling side effects for checkpoint inhibitors based on recommendations by Weber et al⁶³. This guideline is in Danish and named “Vurdering og håndtering af bivirkninger relateret til behandling med ipilimumab, nivolumab og pembrolizumab” and is available online and in print for the physician at duty. In the highly unlikely case that the vaccine induces a cytokine release syndrome, also known as a cytokine storm, the patient will be treated in accordance with the guideline on treatment of cytokine release syndrome recently published by Brudno et al⁶⁴.

Patients will be admitted at the Department of Oncology, Herlev Hospital, in case of occurrence of adverse events related to the investigational treatment that requires hospitalization.

The intensive care unit at Herlev Hospital will be informed of the study, since intensive care support could potentially be required if a treated patient develops anaphylactic shock. The information will be given prior to the start of patient inclusion in the protocol and treatment will not begin before the department management at the intensive care unit has confirmed that the information is received.

Insurance

Patients' participation in the study will be covered by the hospital's liability insurance.

Ethical aspects

This project will potentially add to existing knowledge in the field of immune therapy and help improve treatments and thus prognosis of metastatic solid tumors.

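### No solicited list, diary or planned contact is described between three-weekly visits, so short-lived grade 1-2 reactions may be under-recorded; the adjuvant statements also conflict

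*Combined protocol and SAP*

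**What the plan says.** Objectives and endpoints: "The primary endpoint is adverse events (AE) assessed by Common Terminology Criteria for Adverse Events (CTCAE) 4.0 and laboratory monitoring". The endpoint is not restricted by grade. Under Study design there is one arm of ten patients, all at the same dose.

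The protocol describes how events are found in two places.

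- Protocol synopsis, Assessment of safety: "A systematic recording of AEs will take place during the course of treatment and follow up", and "Recording will take place during patient attendance in the outpatient clinic or at the hospital ward at the Department of Oncology, Herlev Hospital".
- Monitoring of toxicity, Adverse events: "All AEs reported spontaneously by the subject or observed by the investigator or his staff will be recorded". The same section adds a duty: "The investigator must attempt to identify all clinical and objective events from patients receiving treatment".

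The Detailed treatment and evaluation schedule marks CTCAE 4.0 at screening, at each of the 16 vaccine visits and at the final evaluation, with 21 days between visits. Under Procedures regarding treatment, patients are observed for 30 minutes with each of the first three vaccines. After that, "The remainder of vaccines can be administered with observation of the patient for 15 minutes".

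The protocol also makes two kinds of statement about the adjuvant. The Montanide paragraph of the synopsis says that it "does usually not cause any systemic side effects with the dose used in this trial". The Adjuvant section and Known adverse reactions both say: "Frequently reported side effects after injection are flu-like symptoms (headache, chills, fever and nausea"). Those two sections also list common local reactions and call all these reactions generally mild to moderate and, as a rule, short-lived.

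**The concern.** The reactions most to be expected begin after the patient has gone home and may be over before anyone grades them. The only route of detection that the toxicity section names is a report volunteered by the patient or an observation by staff. A fever or a sore arm that has settled cannot be observed three weeks later, and its worst severity can then only be remembered.

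Tolerability is half of the primary objective, the peptide has not been given to humans before, and no control arm shares the same recording loss. If mild reactions go unrecorded, the tolerability profile will look better than it was. The conflicting adjuvant statements add a smaller problem. The investigator must judge relatedness, and the protocol gives two different accounts of what the adjuvant is expected to do.

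**Working it through.** **Step 1. Visit count.** Inputs from Treatment plan: one vaccine every 3 weeks for 48 weeks. 48 / 3 = 16, which reproduces the stated 16 vaccines.

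**Step 2. Interval from dose to next scheduled grading.** The schedule places CTCAE grading on vaccine days, with 21 days between them. For vaccines 1 to 15 the next scheduled grading is at the following vaccine; for vaccine 16 it is at the final evaluation. Grading on the vaccine day itself can cover at most what appears before the patient leaves.

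**Step 3. Direct observation.** Inputs from Procedures regarding treatment:

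- 3 × 30 + 13 × 15 = 90 + 195 = 285 minutes, or 4.75 hours, for a patient who completes treatment.
- Treatment period: 16 × 21 = 336 days; 336 × 24 × 60 = 483,840 minutes.
- 285 / 483,840 = 0.0006, or about 0.06%.

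This observation is aimed at acute allergic reactions. The figure shows only that it cannot stand in for collecting later symptoms; it does not measure what is lost.

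**Step 4. The descriptions side by side.**

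| Question | Synopsis | Later sections |
|---|---|---|
| How are AEs found? | Systematic recording, at attendance | Volunteered or observed, plus a duty to try to identify all events |
| Is a method given for events already over? | None stated | None stated |
| Systemic effects of the adjuvant? | Usually none at the trial dose | Flu-like symptoms frequently reported |

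**Step 5. Size.** The documents give neither a true reaction rate nor a capture rate, so the loss cannot be estimated. The table below is illustration by assumption only: expected patients recorded = 10 × true rate × capture rate.

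| Assumed true rate | Capture 100% | Capture 75% | Capture 50% |
|---|---|---|---|
| 30% | 3.0 | 2.25 | 1.5 |
| 50% | 5.0 | 3.75 | 2.5 |
| 80% | 8.0 | 6.0 | 4.0 |

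With ten patients, a modest recall loss would change the reported frequency by one or more patients in most of these cells. The table does not show that such a loss occurs.

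**The case against.** The strongest reply is that the protocol contains more safeguards than the toxicity section suggests.

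- Attendance includes ward stays, the final evaluation, toxicity evaluations at 3 and 6 months for completers, and the 48-hour reading of the skin test after vaccine 4 unless the patient declines it.
- Patients have phone numbers, a contact doctor and a contact nurse.
- Every vaccine visit includes CTCAE grading, a physical examination, vital signs and a medication review, and treatment is postponed for certain graded events, so staff must consider AEs before each dose.
- Recording an event at a visit does not limit it to events present that day.
- Data collection follows a data source list and an eCRF that are not in the available documents and may contain solicited fields.

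Much of this stands. A reader might infer that AEs are recorded only at three-weekly visits; the contacts above rule that out. A reader might also infer that the synopsis is wrong about the adjuvant. That is not shown either, because its statement is qualified by dose and cites a product summary that is not available here. Nor does it permit staff to omit flu-like symptoms, since AEs are recorded whether or not they are thought related.

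The safeguards do not close the gap. Phone contact depends on the patient calling. The follow-up evaluations come too late for reactions that last days, and the skin test is a single contact. A CTCAE entry at a visit fixes how an event is graded, not how a resolved one is brought to light. The duty to try to identify all events states an aim without a method.

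**Conclusion.** The point holds as a risk to the completeness of the primary endpoint at grade 1-2. In the available text, short-lived flu-like and local reactions depend largely on recall over up to three weeks, and may be under-recorded or under-graded. The two descriptions of how AEs are found differ, and the adjuvant statements are inconsistent and must be reconciled.

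Two stronger conclusions are tempting, and the documents support neither. The first is that tolerability is under-recorded by a stated amount; no capture rate is given, and any percentage would be only the product of assumed inputs. The second is that the safety decision is compromised. The stopping rule and the criterion for calling the treatment safe both count grade 3-4 events, which are less likely to be forgotten, and no effect on that count is shown.

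The conclusion assumes that the data source list and eCRF do not already hold a solicited list. If they do, the remedy reduces to saying so in the protocol. This is a cheap improvement, not a fault that invalidates the design.

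**What to change.** 1. In the synopsis section on assessment of safety and in the Adverse events section, state one method. At every scheduled visit each patient is asked about a fixed list (the reactions under Known adverse reactions, plus fatigue) and about care received elsewhere since the last visit. Worst grade, start date and stop date go into the eCRF. This is in addition to spontaneous reports.
2. Give each patient a one-page card covering temperature, the listed symptoms and worst severity for the days after each vaccine, reviewed at the next visit. Seven days is a reasonable choice, but it is the reviewer's and does not come from the documents.
3. Reconcile the Montanide paragraph of the synopsis with the Adjuvant and Known adverse reactions sections, so that flu-like symptoms are assessed consistently for relatedness.
4. Report solicited and spontaneous events separately, so that more active questioning is not read as worse tolerability.

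The cost is a printed card, a short checklist at visits that already take place and text edits. The downside is a small patient burden and more grade 1-2 events in the tables. No dose, visit or clinical rule changes.
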